### 4. SUMMARY OF STUDY DESIGN

This is a Phase I, single center, randomized, double-blind, placebo-controlled, SAD study of three escalating doses of PTI-125 in healthy male and female volunteers, 18-45 years of age. A total of twenty-four (24) subjects will be enrolled into the study in one of three dose cohorts. Each cohort will contain 8 subjects; six (6) subjects will receive PTI-125 and two (2) will receive placebo in each cohort. Three single ascending doses of PTI-125 oral solution (50, 100, and 200 mg) or placebo solution will be administered to respective cohorts.

The study includes a screening period (Day -28 to Day -1) and an inpatient treatment period (Day 0 through Day 4) and a follow-up visit (Day 7). Subjects will report to clinic the day before dosing and will be randomized to receive either a single dose of orally administered PTI-125 or placebo. Each dose will be administered following an overnight fast of 10 h.

For each dose level, dosing will be staggered such that 2 subjects (one active and one placebo) will be dosed prior to the rest of the group. After a minimum of 24 h and review of all 24-h safety assessments (ECG, brief physical, vital signs and laboratory

---

 Guidance for Industry: Estimating the Maximum Safe Starting Dose in Initial Clinical Trials for Therapeutics in Adult Healthy Volunteers. FDA, CDER, July 2005.

assessments) an independent Data Safety Monitoring Board/Data Monitoring Committee (DSMB/DMC) will determine whether the remaining 6 subjects will be dosed. If safety concerns are raised, 2 additional subjects (randomized according to the Rand schedule to maintain blinding) will be dosed followed by collection and review of the 24-hour safety assessments. The DSMB/DMC will determine after review if dosing will proceed for the remaining 4 subjects.

PK blood samples will be obtained prior to dosing and at specified intervals during the study (0-72 h post-dose). PK parameters will be calculated using non-compartmental analysis.

Blood draws for laboratory testing will be performed prior to dosing and at 24 h post-dose. After safety assessments of ECG, vital signs and a brief physical exam at 72 h, subjects will be discharged from the clinic and will return 7 days post-dose for a final safety assessment.

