#### **4.1 STOPPING CRITERIA**

Dose escalation will be suspended or stopped if any of the following occur and are potentially related to administration of the study drug:

- Clinical signs or symptoms of moderate intensity or greater in two or more subjects
- A single clinical sign or symptom of severe intensity
- AST/ALT elevation greater than 3x upper limit of normal
- Bilirubin elevation greater than 2x upper limit of normal
- Creatinine elevation greater than 1.5x upper limit of normal
- Any significant laboratory finding, confirmed by repeat laboratory testing

The DSMB/DMC may subsequently recommend a second sentinel group to proceed with planned protocol dosing, or termination of the study.

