#### **5.2. INCLUSION CRITERIA**

Each subject must comply with the following criteria:

1. Male or female subjects between 18 and 45 years of age, inclusive.
2. The subject has a body mass index (BMI) within 18-30 kg/m^2 (inclusive).
3. The subject is in good health as determined by medical history and physical examination and clinical laboratory parameters.
4. The subject is willing and able to speak, read, and understand English and provide written informed consent.
5. The subject is a non-smoker for at least 12 months. If a former smoker, the reason for stopping must be evaluated.
6. Females who are physically incapable of childbearing defined as postmenopausal, or surgically sterile (hysterectomy, bilateral tubal ligation, bilateral oophorectomy or an Essure procedure). Appropriate documentation (ex; medical record) of the surgical sterilization procedure to be obtained and held within the subject's study file.
7. The subject must agree to comply with the drawing of blood samples for the PK assessments.
8. The subject is willing and able to comply with all testing and requirements defined in the protocol.
9. The subject is willing and able to remain at the study site unit for the duration of the confinement period and return for the outpatient visit.

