## **6.2. ADMINISTRATION AND DOSING REGIMEN**

All subjects in each cohort (8 subjects) will be randomized to receive PTI-125 (6 subjects) or placebo (2 subjects). Following an overnight fast of at least 10 h, subjects will receive a single oral dose of PTI-125 oral solution or placebo followed by approximately 240 mls of room temperature water. No food will be allowed until 4 h post-dose. Water will be allowed as desired except for 1 h before and 1 h after dosing.

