### **7.1. EVALUATIONS BY VISIT**

#### **7.1.1. *Screening Period***

The following will be completed within 29 days prior to administration of the study medication:

- Informed Consent (written consent must be obtained prior to conducting any screening activities)
- Review of Inclusion and Exclusion Criteria

- Medical history
- Review of concomitant medications
- Physical examination, including measurement of orthostatic vital signs (blood pressure, temperature, pulse and respiratory rate after a 3-min sitting period followed by blood pressure and pulse after a 2-min stand period), height, weight and calculated BMI.
- A 12-lead ECG (5-minute supine)
- Laboratory assessments, including serum chemistry, hematology, and urinalysis; ethanol breath test, urine drug screen, urine cotinine, HIV test, HBsAg and HCV Antibody.
  
- FSH test for female subjects claiming post-menopausal status

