## 10. STATISTICAL CONSIDERATIONS

### 10.1. RANDOMIZATION

Subjects will be assigned to PTI-125 or placebo based on a computer-generated randomization schedule prepared prior to the study. Pain Therapeutics, Inc. (PTI) will interact with the pharmacy to have study drug for each subject labeled according to this randomization code. Randomization Numbers will be used as subject code numbers and will be assigned when qualified subjects are randomized.

The randomization code will not be revealed to study subjects, investigators, clinical staff or study monitors until all subjects have completed therapy and the database has been finalized and closed.

Under normal circumstances, the blind should not be broken. The blind may be broken only if specific emergency treatment is indicated. The date, time and reason for the unblinding must be documented on the case report form, and the medical monitor must be informed as soon as possible.

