#### **10.4. STATISTICAL ANALYSIS**

Comparison of the PK parameters  $C_{max}$ ,  $AUC_{last}$ , and  $AUC_{inf}$  for PTI-125 between treatments will be done using an analysis of variance (ANOVA) model with factors for period and treatment.  $T_{max}$  will be compared among groups using a non-parametric analysis (Wilcoxon Rank Sum or Signed Ranks tests).

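### The between-dose PK comparison in 10.4 is not protected by randomisation and omits body weight; pre-specify a weight-adjusted analysis beside the unadjusted one, and drop the period factor

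*Combined protocol and SAP*

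**What the plan says.** - **Allocation.** Section 10.1: "Subjects will be assigned to PTI-125 or placebo based on a computer-generated randomization schedule prepared prior to the study". Section 6.2: "All subjects in each cohort (8 subjects) will be randomized to receive PTI-125 (6 subjects) or placebo (2 subjects"). Neither section describes random assignment to a dose level.
- **Dose levels.** Section 4: "A total of twenty-four (24) subjects will be enrolled into the study in one of three dose cohorts", and "Three single ascending doses of PTI-125 oral solution (50, 100, and 200 mg) or placebo solution will be administered to respective cohorts". Section 4.1 makes the steps conditional: "Dose escalation will be suspended or stopped if any of the following occur and are potentially related to administration of the study drug". The cohorts are therefore filled in sequence, at fixed mg doses.
- **Model.** Section 10.4 compares Cmax, AUClast and AUCinf "for PTI-125 between treatments will be done using an analysis of variance (ANOVA) model with factors for period and treatment". It names no weight, BMI or sex term. Section 7.2.2 has only one sample per placebo subject analysed, so the treatments being compared can only be the three PTI-125 doses.
- **Body size.** Section 5.2 admits both sexes and sets one limit on size: "The subject has a body mass index (BMI) within 18-30" kg/m². Section 7.1.1 records "height, weight and calculated BMI" at screening. Section 10.3 lists Cl/F and Vz/F without a per-kg version.
- **Purpose.** Section 3 states safety and pharmacokinetics as the objective, with no dose-proportionality hypothesis.

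**The concern.** The dose comparison is between groups of six people recruited one group after another. If the later group is heavier on average and exposure at a fixed dose falls with weight, that group's exposure is lower for a reason unrelated to dose. The model in 10.4 would assign that difference to treatment.

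What is at stake is the reading of how exposure rises over 50, 100 and 200 mg. A departure from proportionality could appear or be hidden. Weight is already collected, so an adjustment needs no new procedure. It should be written down in advance, because a covariate chosen after the imbalance has been seen looks selective.

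**Working it through.** **1. The plan's own count.** 3 cohorts × (6 + 2) = 24 subjects, which agrees with sections 4, 5.1 and 10.6. Of these, 3 × 6 = 18 are active and enter the between-dose comparison. Section 10.6 gives no CV, alpha, power or effect size, so no statistical derivation can be reproduced.

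**2. The period factor.** Each subject receives one dose. If period means dosing occasion, it is constant. If it means cohort, the design matrix has 1 intercept + 2 period + 2 treatment = 5 columns but rank 3, so period and dose are fully aliased. The estimable model is one-way by dose, with 18 − 3 = 15 error df, or 14 with one covariate.

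**3. Possible weights.** Weight = BMI × height². At assumed heights of 1.60 m and 1.80 m, BMI 18-30 allows 46-77 kg and 58-97 kg. This is the spread of individuals, not of means of six.

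**4. Effect of a given gap in mean weight.** Assume exposure is proportional to weight^−b with b = 0.75 or 1, and mean weights of 80 and 66 kg. Then ln(80/66) = 0.192.
- b = 0.75: exp(−0.75 × 0.192) = 0.866, a shift of about 13%.
- b = 1: 66/80 = 0.825, a shift of 17.5%.

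If the higher-dose cohort is the heavier one, a true twofold ratio appears as 2 × 0.866 = 1.73 or 2 × 0.825 = 1.65. It still rises.

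**5. How often chance alone gives such a gap.** The SE of a difference in mean ln(weight) is SD × √(2/6). For an assumed SD of 0.15-0.20 this is 0.087-0.115. A gap of 0.192 or more in either direction has probability 3-10% for a given pair of cohorts, and 7-22% for at least one of the three pairs.

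**6. Coverage and width (simulation).** 18 subjects, log scale, b = 0.75-1, SD of ln(weight) 0.15-0.20, total CV 25-40%.

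| Setting | Unadjusted coverage of 95% CI | Adjusted coverage | CI half-width, adjusted/unadjusted |
|---|---|---|---|
| No systematic gap | about 95% | about 95% | 0.61-1.00 |
| 80 v 66 kg gap imposed | 75-91% | about 95% | 0.66-1.15 |

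The adjusted coverage is what one would expect, because the fitted model is the one that generated the data. The largest gain in width needs b = 1, SD 0.20 and CV 25%, where weight explains 0.04/0.0606 = 66% of the variance.

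**7. If weight matters little.** With b = 0 or 0.25 and CV 30%, the adjusted interval is about 3-4% wider without a gap and 11-20% wider with the 80 v 66 kg gap.

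**8. Drift over cohorts.** F-test on dose-normalised log AUC with weight CV 15%, b = 0.75, other log-SD 0.25 and 20,000 runs. When mean weight rises by 0, 10, 20 or 30% from first to last cohort, the unadjusted false-positive rate is 4.9, 6.5, 9.9 and 16.2%. With ln(weight) in the model it is 4.9-5.0% throughout.

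**9. Scale for comparison.** At an assumed between-subject CV of 30%, the log-SD is √ln(1.09) = 0.294. The half-width with 15 df is 2.131 × 0.294 × √(2/6) = 0.361. The unadjusted 95% CI around a twofold ratio is then 2/1.435 to 2 × 1.435, or 1.39 to 2.87.

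**The case against.** A reader might infer that any weight or sex difference between the cohorts will be read as a dose effect. The documents do not support that. Random differences in weight between subjects are part of the between-subject variance in the ANOVA residual, and without a systematic gap the unadjusted interval and test keep their nominal levels. Bias needs a shift in recruitment between cohorts. The plan neither shows nor excludes one, and all cohorts share one site and one set of entry criteria. The coverage of 75-91% is conditional on an assumed gap, and the documents give no relation between weight and exposure.

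A reader might also infer that the lack of randomisation to dose is a design error. It is inherent in dose escalation, and section 3 states no proportionality hypothesis that it would undermine. A shift of 13-18% is small against dose steps of 100% and lies inside the illustrative interval of 1.39 to 2.87.

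On sex, women must be aged 18-45 and postmenopausal or surgically sterile, which probably limits their number. If 20% of subjects were women, two cohorts of six would differ by three or more in about 7% of cases. Sex was not modelled here.

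All of this stands, and it keeps the point minor. It does not remove it: long-run error control is little help to someone interpreting one trial with a visible imbalance, and the data needed to deal with it are already collected.

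**Conclusion.** The point holds as a low-cost improvement. Randomisation does not protect the comparison in 10.4, and the model leaves out a body-size measure that the trial records while dosing in fixed mg. For an assumed 80 v 66 kg gap and an exponent of 0.75-1, a dose ratio is distorted by about 13-18%. That is enough to blur dose proportionality, not to produce a dose trend. Without a systematic gap the planned comparison is not biased by weight. The weight SD, exponent, PK CV and heights are assumptions, not figures from the plan. The period factor is a separate fault in the same sentence. It does not depend on these assumptions and has to be corrected before any covariate is added.

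**What to change.** In section 10.4:
- Remove the period factor and analyse log-transformed Cmax, AUClast and AUCinf in a model with dose as the factor.
- Pre-specify a second analysis adding ln(screening weight) as a covariate, reported beside the unadjusted result whichever way it falls.
- Tabulate weight and sex by cohort, and report Cl/F and Vz/F also per kg.
- Describe the between-dose comparison as non-randomised and exploratory.

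The cost is a few lines of text and one error df (15 to 14), with no new procedure. The adjusted interval is 0-39% narrower without a weight gap in the settings where weight matters. If weight explains little, it is about 3-4% wider without a gap and up to about 20% wider with one, which is why the unadjusted result should stay alongside.

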### 3. STUDY OBJECTIVES

The objective of this study is to determine the safety and pharmacokinetics of PTI-125 following single-dose oral administration in healthy male and female normal volunteers, age 18 - 45.

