### 7.2.2. *Preparation of Plasma Samples for Pharmacokinetic Determination*

At each blood collection, blood samples (4 mL) will be drawn into a Vacutainer® tube containing K2EDTA. The tubes will be placed on ice. Within 30 minutes of collection, the blood will be centrifuged at approximately 1000 X G for 15 minutes between 4-5°C. Within 30 minutes of centrifuging, plasma (at least 1.5 mL) will be split evenly into two aliquots, transferred to polypropylene tubes and stored at

approximately -70°C or below until analysis. The time from sample collection to storage should not exceed 60 minutes.

At the end of the study the samples will be shipped frozen on dry ice to: Worldwide Clinical Trials Bioanalytical Sciences, [name] for bioanalytical analysis of PTI-125 with a validated assay. Remaining samples following the analysis of PTI-125 are to be retained until directed for disposition by PTI. All samples from PTI-125 subjects will be analyzed. One sample around the Cmax from each placebo subject will be analyzed, such as 40 min, 1 or 2 h. All secondary samples will be shipped to Worldwide Clinical Trials Bioanalytical Sciences upon confirmation of receipt of the primary samples.

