### 10.3. PHARMACOKINETIC PARAMETERS

PK parameters for PTI-125 will be calculated using non-compartmental methods in WinNonlin. The peak drug concentration ( $C_{max}$ ), the time to peak drug concentration ( $T_{max}$ ),  $T_{last}$  and  $C_{last}$ , the time to and concentration of the last quantifiable drug concentration, will be obtained directly from the data without interpolation. The following parameters will be calculated: the elimination rate constant ( $\lambda_z$ ), the terminal elimination half-life ( $T_{1/2}$ ), the AUC from time zero to the time of the last quantifiable concentration ( $AUC_{last}$ ), the AUC from time zero extrapolated to infinity ( $AUC_{inf}$ ), and the percentage of  $AUC_{inf}$  based on extrapolation ( $AUC_{extrap}(\%)$ ),  $Cl/F$ , the apparent oral clearance, and  $V_z/F$ , apparent volume of distribution.

In the pharmacokinetic analysis, BLQ concentrations will be treated as zero from time-zero up to the time at which the first quantifiable concentration was observed; embedded and/or terminal BLQ concentrations will be treated as "missing". Full precision concentration data (not rounded to three significant figures) and actual sample times will be used for all pharmacokinetic and statistical analyses. Nominal sampling times will be used to prepare concentration versus time profiles.

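### Section 10.4 analyses a one-dose-per-subject parallel study with a period factor and a paired-test option, and compares exposure across a 4-fold dose range without a stated scale or dose normalisation

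*Combined protocol and SAP*

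**What the plan says.** Section 10.4 is the only formal PK comparison in the plan. For Cmax, AUClast and AUCinf the comparison "between treatments will be done using an analysis of variance (ANOVA) model with factors for period and treatment". For Tmax it gives a choice: "Wilcoxon Rank Sum or Signed Ranks tests". It states no analysis scale, dose normalisation, hypothesis or significance level, and does not say which groups are paired off for Tmax.

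The design sections describe something simpler. Section 4 has 24 subjects "enrolled into the study in one of three dose cohorts", eight per cohort, six on active drug and two on placebo. Under Section 6.2, "subjects will receive a single oral dose of PTI-125 oral solution or placebo". Section 4 adds that within each cohort "dosing will be staggered such that 2 subjects (one active and one placebo) will be dosed prior to the rest of the group".

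Three other places bear on the point:

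- Section 7.2.2: one sample near the expected peak "from each placebo subject will be analyzed", so placebo subjects have no PK profile.
- Section 3: the aim is to "determine the safety and pharmacokinetics of PTI-125 following single-dose oral administration". Dose proportionality is not named.
- Section 10.6: the sample size is attributed to within-subject variability of log-transformed data from earlier studies of other compounds. This is the only mention of a log scale.

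**The concern.** A period factor and a signed-rank test belong to a crossover, where each subject is measured on more than one occasion. Here nobody is. The within-subject variability cited in Section 10.6 fits the same crossover pattern, and one dose per subject cannot estimate it.

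Two things follow. First, period has to be given a meaning before the model can be fitted, and the meaning decides whether a dose effect adjusted for period exists. Second, since placebo contributes no PK parameters, the treatments compared are 50, 100 and 200 mg. Without normalisation the natural F-test asks whether exposure is equal across a 4-fold range of dose. Nobody expects that it is, and the answer says little about how exposure changes with dose.

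At stake is whether the formal comparison is reproducible from the plan and informative once run.

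**Working it through.** **Design count.** 3 cohorts x (6 active + 2 placebo) = 24, the stated enrolment. Every subject is used once, so there are 18 active subjects with PK profiles, 6 per dose, and 0 within-subject pairs. The signed-rank test cannot be run.

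**What period does to the dose effect.** Degrees of freedom (df) for dose after period = rank(intercept, period, dose) - rank(intercept, period), for the 18 active subjects:

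| Reading of period | Rank without dose | Rank with dose | Dose df after period | Residual df |
|---|---|---|---|---|
| Constant (one period) | 1 | 3 | 2 | 15 |
| Sentinel versus main dosing, 1 + 5 active per cohort | 2 | 4 | 2 | 14 |
| Cohort | 3 | 3 | 0 | 15 |
| Calendar dosing day, 6 levels nested in cohort | 6 | 6 | 0 | 12 |

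The last row assumes one sentinel day and one main day per cohort. Placebo subjects cannot break the aliasing, because they have no Cmax or AUC to enter.

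**What the unnormalised comparison can show.** The documents give no CV, so a range is assumed. Other assumptions: period omitted, 6 per dose, log-normal data, 5% level, and exposure proportional to dose^b with b = 0.7, 1 or 1.3.

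- Log-scale SD: sigma = sqrt(ln(1 + CV^2)) = 0.198, 0.294, 0.385, 0.472, 0.555 for CV 20% to 60%.
- Adjacent doses differ by b ln 2 on the log scale, so the noncentrality of F(2,15) is 6 x 2 x (b ln 2)^2 / sigma^2 = 12 (b ln 2)^2 / sigma^2.
- Example: b = 0.7, CV 50%: 12 x (0.7 x 0.693)^2 / 0.472^2 = 12.7, giving 82.7% rejection.

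Rejection rates (%) for b = 0.7 / 1 / 1.3:

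| CV | Log scale (exact) | Raw scale (100,000 simulated trials per cell) |
|---|---|---|
| 20% | 100 / 100 / 100 | 100 / 100 / 100 |
| 30% | 99.8 / 100 / 100 | 99.5 / 100 / 100 |
| 40% | 95.0 / 99.9 / 100 | 91 / 99.5 / 100 |
| 50% | 82.7 / 98.8 / 100 | 74 / 95 / 99 |
| 60% | 68.7 / 94.7 / 99.7 | 57 / 85 / 96 |

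Reading period as sentinel versus main dosing hardly changes this. The split is balanced over doses, so only the residual df fall: 99.7 / 100 / 100 at CV 30% and 82.1 / 98.7 / 100 at CV 50%.

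The unstated scale matters in its own right. With equal CV and proportional exposure, the raw SD at 200 mg is 200/50 = 4 times that at 50 mg, against the equal-variance assumption of the ANOVA.

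**What estimation would deliver from the same data.**

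- Log-log slope: Sxx = 12 x (ln 2)^2 = 5.765, square root 2.401. The 90% half-width is t(0.95, 16) x sigma / 2.401 = 1.746 x 0.294 / 2.401 = 0.21 at CV 30%, and 0.34 at CV 50%.
- Ratio of two doses: the 90% interval is the estimate times or divided by exp(t(0.95, 15) x sigma x sqrt(2/6)), with t = 1.753. The factor is 1.35 at CV 30% and 1.61 at CV 50%.
- Example: at b = 0.7 the dose-normalised 200/50 ratio is 4^(-0.3) = 0.66. Its 90% interval is about 0.49 to 0.89 at CV 30% and 0.41 to 1.06 at CV 50%.
- At b = 0.7 the slope interval excludes 1 in 76% of trials at CV 30% and 43% at CV 50% (noncentral t, 16 df).

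**The case against.** The strongest reply is that this is leftover wording of little consequence. An analyst would see the aliased factor and drop it, and if dose is entered before period it keeps 2 df under every reading. Rank Sum, the other Tmax option, is valid for pairs of doses, and a signed-rank test with no pairs cannot yield a wrong answer. Section 10.4 names no F-test, so ratios with intervals could equally be what is meant. In every simulated case exposure truly differs between doses, so each rejection is correct: the rates are power, not error. Proportionality is not an objective. Section 10.3 already lists Cl/F, "the apparent oral clearance", which is dose over AUCinf and so carries the dose-normalised information for that parameter. On the log scale normalisation only shifts contrasts by known constants.

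Much of this is fair and limits the importance of the point. It does not rescue the text. Dropping period, or choosing an order of entry, is a decision the plan does not make and would leave until data are in hand. The rejection rates are offered as evidence of an uninformative comparison, not of a false-positive problem, and they do rest on reading the ANOVA as an F-test. Cl/F covers neither Cmax nor AUClast. The remark that normalisation is a mere shift holds on the log scale only, and Section 10.4 does not choose that scale; the mention in Section 10.6 hints at it without prescribing it.

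**Conclusion.** The concern holds. The period factor and the Signed Ranks option are wrong for the design, which follows from the documents alone without any assumption. The missing scale, normalisation and purpose leave the comparison poorly defined. Two analysts following Section 10.4 could report no dose effect adjusted for period, or a test that rejects in at least 99% of trials at CV up to 30% for any of the three dose-exposure relations tried. At CV 50% to 60% the rates spread (log scale, 68.7% to 100%), but separation is only partial. These rates depend on assumed CVs, log-normal data, the 5% level and period being left out.

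The reach is limited. The parameters in Section 10.3, the safety summaries and the escalation rules in Section 4.1 do not use Section 10.4. The plan should be corrected, but the study's main outputs do not hang on it.

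**What to change.** Revise Section 10.4 as follows:

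1. Remove the period factor.
2. Remove the Signed Ranks option for Tmax and state which dose pairs the Rank Sum test compares.
3. Analyse ln(Cmax), ln(AUClast) and ln(AUCinf) with dose as the only factor.
4. Report dose-normalised geometric mean ratios (100/50 and 200/50) with 90% confidence intervals, and/or the slope of ln(parameter) on ln(dose) with its 90% interval. Present these as estimates, not as a pass/fail test of proportionality. The ratios come from the fit in item 3 after subtracting ln 2 or ln 4.

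With 6 subjects per dose the estimates will be imprecise, and the gain is modest if variability is high. They would still show the size and direction of any departure from proportionality, which the present comparison does not. The cost is a few sentences in Section 10.4 and a few lines of analysis code, with no new subjects, samples or procedures.
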